12. STATISTICAL AND ECONOMIC CONSIDERATIONS

Sample sizes sought in the four randomised comparisons

The sample sizes sought for the four comparisons have been based on a number of considerations. They have drawn on the relationship between changes in the OKS and other well known outcome instruments, and what previous research has suggested is plausible. They have also taken account of clinical issues, such as the size of differences that seem likely judged on current experience, the possibility of adverse effects, and cost differences.

The table describes the statistical power to detect differences of 1.5, 3.0 and 4.5 in the mean OKS for three sample sizes (700, 350, and 175 in each group), firstly with an alpha error of $2P < 0.01$ and secondly for an alpha error of $2P < 0.05$. These calculations assume a standard deviation for the OKS of 10 points.

Table 3 Statistical power to identify differences of 1.5, 3.0 and 4.5 in mean OKS for three sample sizes, at two levels of statistical significance.

Mean difference in OKS	1.5		3.0		4.5		
	2P<0.01	2P<0.05	2P<0.01	2P<0.05	2P<0.01	2P<0.05	
Number in	700	60	80	>99	>99	>99	>99
each randomised	350	<50	50	91	97	99	>99
group	175	<50	<50	60	80	94	98

Although the OKS is the principal outcome, possible differential effects on revision rates have also been considered where appropriate. Although these are presented here as simple rate differences, these analyses will in fact be able to identify smaller differences with the same statistical power as that indicated. There are two reasons. First, these analyses will be based on the time to revision using prosthesis 'survival curves' rather than a simple dichotomous variable. Second, survival curves will also be generated for a composite outcome which includes patients whose knee prostheses are judged (by falling below a predefined threshold on the Oxford score) to have failed, in addition to those who actually had revision (thus increasing the number of 'events', and hence statistical power).

(i) Metal backing of tibial component

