The concern in this comparison is that loosening of non-metal backed tibial components may lead to severe symptoms in the long-term. The aim therefore is for a sample size which is large enough to identify a difference equivalent to a typical category change in the American Knee Society Score (that is, a difference of about 3.0 in the OKS). This will require a minimum of 175 per group to have reasonable power (80%) with an alpha error of 2P<0.05 (see Table). A comparison with 235 in each group, for example, would have 90% power to identify this difference.

(ii) Patellar resurfacing

Based on preliminary results of follow-up of a small randomised trial - currently unpublished - comparing patellar resurfacing with no resurfacing, the effect of resurfacing, if it exists, is likely to be relatively small and near a difference in the mean OKS of 1.5. The table shows that a trial with 700 in each group would have 80% power to identify this difference (2P<0.05). A trial of this size (about 1500 people) would also have reasonable

power to identify differences in revision rates over prolonged follow-up - more than 90% power to detect a halving from 10% to 5%, for example.

(iii) Uni-compartmental arthroplasty

A non-randomised comparison of two cohorts characterised by management with either a uni-compartmental prosthesis or total knee replacement showed a difference in the mean OKS scores of 3.4, whereas follow-up of similar but smaller randomised cohorts suggested a smaller difference of 1.6, albeit with a wide confidence interval. The aim is therefore for a trial with at least 175 participants in each group, so that there is a good chance of identifying a difference in the mean OKS of 3.0. There may be higher revision rates after uni-compartmental arthroplasty. A trial of this size would have 90% power to identify an increase from 5% to 15% in this respect.

(iv) Mobile versus fixed bearing arthroplasty

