The type of economic analysis performed for each comparison will depend on the findings. If there are no differences in outcome for a particular comparison, cost minimisation analysis will be used. If differences emerge, cost-effectiveness analyses from a societal perspective will be performed. The primary measure of effectiveness will be pain and function as assessed by the Oxford Knee Score. Information on utilities will also be available for analysis because trial patients will also complete EQ-5D for which population-weighted values are available.

Costs of alternative forms of knee-replacement surgery may be considered as either short term or long term. In the short term, differences in costs of alternatives will arise from differences in surgical procedure, technology, forms of care during hospital stay, length of hospital stay and short-term complications (wound infection, deep vein thrombosis, pulmonary embolism). In the long term, major differences in costs of the surgical alternatives will arise in relation to differences in longer term outcomes, particularly recurrence of pain and physical dysfunction requiring further primary, community and hospital care, and, in some cases, need to revise surgery.

Three data gathering components will be used to address these major sources of variation in costs (i) early (ii) medium to long term and (iii) modelling.

(i) Early data collection

Cost generating events in the short term will be recorded by means of a patient-specific checklist administered by research nurses at the participating hospitals, using theatre records and hospital notes. This will cover time in theatre and on ward, surgical procedure(s), diagnostic and investigative procedures and tests, and duration and intensity of rehabilitation.

(ii) Medium to long-term data collection

Following initial hospitalisation, information on health care resources used will be recorded using questions integrated into the main follow-up questionnaire administered to all patients annually. This will estimate annual numbers of knee-related primary care

consultations, out-patient visits, and use of other health care services. Full information on all subsequent in-patient admissions for investigative procedures or revision surgery will be recorded using the research nurse system described elsewhere in this protocol.

(iii) Modelling

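### The economic analysis switches to cost minimisation when no outcome difference is found, in a trial sized only to detect differences, so a non-significant result is likely to stand in for equivalence

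*Protocol*

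**What the plan says.** The Economic evaluation part of protocol Section 12 opens: "The type of economic analysis performed for each comparison will depend on the findings". It then sets two branches. The first is "If there are no differences in outcome for a particular comparison, cost minimisation analysis will be used". The second is "If differences emerge, cost-effectiveness analyses from a societal perspective will be performed". On the effect measure it says: "The primary measure of effectiveness will be pain and function as assessed by the Oxford Knee Score". EQ-5D utilities are also to be available.

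The same section sizes each comparison by its power to detect a difference in mean OKS. For comparison A, with a target of 3.0 points: "This will require a minimum of 175 per group to have reasonable power (80%) with an alpha error of 2P<0.05". Comparison D also plans at least 175 per group for 3.0 points, C plans 350 per group for 3.0, and B plans 700 per group for 1.5. No equivalence or non-inferiority margin appears anywhere in the protocol.

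The one explicit promise to report uncertainty in the economic section concerns the model that extends results beyond follow-up. The protocol Summary lists the worth of any additional NHS cost among the three bases for judging each comparison.

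**The concern.** Two observed means are never exactly equal, so a rule that acts on an absence of difference needs a criterion. The protocol states none, and the only decision tool its design supplies is a test for a difference. If that test drives the switch, a comparison too imprecise to answer the question is handled as though the effect had been shown to be zero. The estimated OKS and quality-adjusted life-year (QALY) differences, their uncertainty and their correlation with cost then drop out of the economic comparison, and the policy with the lower total cost is preferred by default.

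What is at stake is one of the trial's three stated aims. Whether an extra cost is worth paying depends on how much benefit the data allow, and a method that fixes the benefit at zero cannot show that.

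**Working it through.** **Inputs (protocol Section 12).** SD: "These calculations assume a standard deviation for the OKS of 10 points". Two-sided alpha 0.05. Planned numbers and targets as above. Recruitment aims of at least 1500, 750 and 400, which are 750, 375 and 200 per group if nobody is lost. For D, the section cites a difference of 1.6 from small randomised cohorts.

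**Formulas (normal approximation, equal groups).**
- SE = 10 × √(2/n)
- Power = Φ(d/SE − 1.96), ignoring the negligible far tail
- P(non-significant) = 1 − power
- 95% CI half-width = 1.96 × SE

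**Step 1: reproduce the stated powers.**
- 175 per group, 3.0 points: SE = 1.069, Φ(2.806 − 1.96) = 80.1% (stated 80%).
- 350 per group, 3.0 points: SE = 0.756, Φ(3.969 − 1.96) = 97.8% (stated 97%).
- 700 per group, 1.5 points: SE = 0.535, Φ(2.806 − 1.96) = 80.1% (stated 80%).

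The protocol's figures hold.

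**Step 2: chance of a non-significant OKS result when a real difference exists.**

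| Comparison | True difference | n per group | P(non-significant) | n if no loss | P(non-significant) |
|---|---|---|---|---|---|
| A and D | 3.0 (target) | 175 | 19.9% | 200 | 14.9% |
| B | 1.5 (target) | 700 | 19.9% | 750 | 17.2% |
| C | 3.0 (target) | 350 | 2.2% | 375 | 1.6% |
| D | 1.6 (cited) | 175 | 67.8% | 200 | 64.1% |

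**Step 3: what a non-significant result would rule out.** Half-widths are 1.96 × 1.069 = 2.10 points at 175 per group, 1.48 at 350 and 1.05 at 700. At 175 per group a result is non-significant whenever the observed difference is under 2.10 in size. The interval still reaches 3.0 once the observed difference exceeds 3.0 − 2.10 = 0.90.

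As an illustration, take each comparison's target difference as an equivalence margin (an assumption, since the protocol gives no margin) and let the true difference be zero. The chance that the 95% CI lies wholly inside the margin is:
- A and D (±3.0, 175 per group): 2Φ(0.905/1.069) − 1 = 60%
- B (±1.5, 700 per group): 2Φ(0.452/0.535) − 1 = 60%
- C (±3.0, 350 per group): 2Φ(1.518/0.756) − 1 = 96%

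A zero true difference is non-significant 95% of the time. So in A, B and D about 95 − 60 = 35% of such trials would be non-significant while the interval still contains the target difference.

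**Step 4: which margins are usable.** At 175 per group a margin of 1.5 can never be met, because the half-width of 2.10 already exceeds it. At 350 per group it would be met only about 2% of the time, even with a true difference of zero.

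**The case against.** The strongest reply is that the economic section names no p-value, test or deciding outcome, and that an analysis plan, not shown here, may say how an absence of difference will be judged. A reader might infer that the phrase can only mean a non-significant test. The text does not establish that, although it is the likely working reading given the design. The missing criterion is not itself the finding. What remains is that the protocol fixes a results-dependent switch, and a plan that estimated cost and effect jointly for every comparison would depart from it.

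Four further points limit the claim:

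- **Other outcomes.** A reader might take 1 − power as the rate at which comparisons would be analysed on cost alone. The trigger refers to outcome in general, and the protocol also collects EQ-5D, SF-12, revision and survival. If a difference in any of these opens the cost-effectiveness branch, the Step 2 figures are upper bounds.
- **Which option is favoured.** A reader might infer that the rule favours the cheaper implant. Costs include hospital stay, complications, later care and revision surgery, so it favours the policy with the lower total cost. A dearer implant with fewer revisions could win.
- **Uncertainty.** A reader might infer that the whole economic section ignores it. Uncertainty is to be reported for the extrapolation model, and the dummy tables show OKS and EQ-5D by arm. The gap is confined to the within-trial cost-minimisation branch.
- **Choice of example.** At 175 per group a true 1.5-point difference is non-significant in 71% of trials. That pairs B's target with the numbers for A and D. B is planned at 700 per group, where the figure is 20%.

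The rule also leaves allocation, sample size, data collection and the clinical analyses untouched.

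**Conclusion.** The concern holds as a defect in the economic rule. The protocol lets the findings decide whether effect is estimated or taken as zero, and nothing in it separates a demonstrated absence of difference from a failure to detect one.

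If OKS significance at the 5% level decides, a real difference of the target size would go to the cost-only branch in at most about 20% of trials for A and D (about 15% if all 200 per group are analysed) and about 20% for B. For C it would be only about 2%, so the rule does little harm there at 3.0 points. For the smaller difference the protocol itself cites for D, the figure is about 68%.

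These figures rest on the SD of 10, the planned numbers and the normal approximation. The protocol says death and loss are hard to predict. Loss of more than 25 of 200 per group (12.5%) would take A and D below 175 and raise their figures.

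**What to change.** Delete the conditional rule. For every comparison, whatever the clinical p-value, estimate incremental cost and incremental effect jointly (OKS, and QALYs from EQ-5D) and report both with their uncertainty. Bootstrap or net-benefit methods would serve; the choice can be left to the analysis plan.

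If cost minimisation is kept, make it a secondary presentation only. Use it when the confidence interval for the effect lies wholly within a margin stated in advance, and choose a margin that the comparison's sample size can meet. Step 4 shows that 1.5 points cannot serve for A or D at 175 per group and would almost never be met for C.

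The cost is a wording change and a little more analysis, made before the economic analysis begins. OKS, EQ-5D and resource use are already to be collected, and no sample size changes.

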kat

PROTOCOL

VERSION 4 – June 2001

SUMMARY

AIMS

This study addresses questions about four developments in knee replacement surgery:

- Is a metal backing plate for the tibial component of the total knee replacement better than a single high density polyethylene component?
- Is it better to resurface the patella as part of a knee replacement or not?
- Does a polyethylene moving component (bearing) between the tibia and femur have a better outcome than standard designs without a moving bearing?
- Is it better to replace a single component of the knee or to replace the whole knee joint?

The assessment of outcome for each of the comparisons is based on:

- Patient-assessed function and health status
- Reoperation rates
- The 'worth' of any additional cost to the NHS

BRIEF OUTLINE OF THE STUDY

Surgeon participants

Surgeons may opt to take part in any (or all) of the comparisons for which they have no clear preference for one of the options.

Patient eligibility

Any patient who requires a knee replacement, and who the surgeon feels would be eligible for the trial.

Information and randomisation

Individual patients will be entered into no more than two possible permutations of the study. Prior to admission to hospital, patients will be sent information about the study, inviting them to take part, and describing the possible options for their operation. If they agree to take part, they will be randomised around the time they are admitted to hospital for their operation. Randomisation will be carried out by the central Trial Office.

Data collection

During their hospital admission, standard information will be collected on the patient's operation and recovery, including short-term complications and data relating to their hospital stay.

Three months and annually after their operation, patients will be sent postal questionnaires asking about their general health, their knee function, and their use of the health service, including any re-admissions and revision surgery. Follow-up will continue for up to eleven years after their operation, to ensure that the long-term performance of the knee operation is properly assessed.

Practical arrangements in clinical centres

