7. OUTCOME ASSESSMENT

Participation does not require any special tests or extra hospital visits (over and above standard care).

Most data describing outcomes will be collected directly from participants through postal questionnaires. The same questionnaire will be completed at three months and then annually (Appendix 5). It will include:

- the Oxford Knee Score (a twelve-item instrument measuring patients' perceptions of pain and function).
- the SF-12 (an abbreviated form of the SF-36, explaining more than 90% of the variance of the SF36).
- the EQ-5D (to derive quality-adjusted life years, QALYs).
- questions about any further hospital admissions and surgery.

Clinical data will be collected in a standardised way from casenotes to describe operative complications, and any further surgery, especially for revision.

Participants will be flagged at the Office for National Statistics for notification of death registration (and possible later tracing if contact has been lost during follow-up).

Follow-up is planned for at least ten years.

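### Section 12 promises a societal perspective for cost-effectiveness where outcomes differ, but every data source the protocol describes covers health care costs only

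*Protocol*

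**What the plan says.** The economic part of Protocol Section 12 has two branches. If a comparison shows no difference in outcome, a cost-minimisation analysis is planned, and no perspective is named for it. If differences emerge, "cost-effectiveness analyses from a societal perspective will be performed".

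The Aims in the Summary give three bases for judging each comparison, and the cost basis is the worth "of any additional cost to the NHS".

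Section 12 then sets out how costs will be captured:

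- **Early:** a checklist completed by research nurses from hospital records. "This will cover time in theatre and on ward, surgical procedure(s), diagnostic and investigative procedures and tests, and duration and intensity of rehabilitation".
- **Medium to long term:** "information on health care resources used will be recorded using questions integrated into the main follow-up questionnaire", with later in-patient admissions recorded by the research nurses.
- **Modelling:** an extension beyond follow-up, with parameters set from the trial's own data.

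Unit costs are to be found for the events captured in this way, from the centres and from national sources.

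**The concern.** A societal perspective counts costs whoever bears them. For knee replacement that would include patients' own expenses, unpaid care by family, and lost work, in addition to health care. If those items are not collected, the calculation yields a health-service cost whatever it is called.

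At stake is what the economic result can claim. Value for money is one of the three bases on which each comparison is judged. A reader told that a result is societal would take it that costs outside the health service had been measured and weighed. On the data described, any difference between arms in those costs would simply be absent from the result.

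**Working it through.** No figure is stated on this point, so there is nothing to reproduce or recompute. The check sets the promised perspective beside each place in the Protocol that describes resource use or costing.

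1. **Where cost differences are expected (Section 12, Economic evaluation).** In the short term, the sources named are the procedure, the technology, care and stay in hospital, and early complications. In the long term they are recurring problems "requiring further primary, community and hospital care, and, in some cases, need to revise surgery". All are health care. Community care, even read broadly, does not extend to costs borne by patients or carers, or to lost work.

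2. **Early data (Section 12 (i)).** Theatre and ward time, procedures, tests and rehabilitation, taken from theatre records and hospital notes. These are hospital resources only.

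3. **Medium to long-term data (Section 12 (ii)).** Knee-related primary care consultations, out-patient visits, other health care, and nurse-recorded admissions. Health care only.

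4. **Modelling (Section 12 (iii)).** Parameters come from what the trial observes on revisions, resources and risk factors. This extends the same data in time and brings in no new kind of cost.

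5. **Unit costs (end of Section 12, Economic evaluation).** Prices are sought for the events already listed. An item that is not recorded is therefore not valued.

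6. **Other descriptions of the questionnaire.** The Summary describes postal questionnaires "asking about their general health, their knee function, and their use of the health service, including any re-admissions and revision surgery". Section 7 lists, beside the Oxford Knee Score, SF-12 and EQ-5D, only "questions about any further hospital admissions and surgery". The follow-up letters to participants ask about medical services used.

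7. **Dummy Table 5A.** The resource rows are readmission, further knee surgery, and visits to the GP, the orthopaedic out-patient clinic and the physiotherapist.

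Of the three data components that Section 12 names (early, medium to long term, modelling), 0 of 3 are described as reaching beyond health care. Patient expenses, travel, time off work, lost productivity and informal care are not mentioned as cost items anywhere in the Protocol.

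**The case against.** Several objections deserve weight.

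**The forms are not shown.** A reader might infer that the societal analysis is impossible. The documents do not support that. The participant questionnaires (Appendix 5) and the surgeon, hospital and participant forms (Appendix 6) are listed, but their items are not visible. The Protocol's own summaries of the questionnaire are also incomplete: Section 7 names only admissions and surgery as resource use, while Section 12 adds primary care, out-patient and other health care questions. Silence in a summary does not prove that an item is missing from the form. This stands, and it limits the point to the data that the Protocol describes.

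**The promise is conditional.** The societal perspective applies only where outcomes differ. That is correct. But it is also the situation in which a cost-effectiveness result would inform a choice between prostheses.

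**The Aims do not exclude a wider view.** Cost to the NHS is one of three bases for assessment, and an economic analysis could look further. This largely stands. The Aims are supporting context, and the main evidence is the mismatch within Section 12 itself.

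**The dummy tables are weak evidence.** They are dated October 1999, before Version 4 of June 2001, and none is a cost table. That is fair, and the point does not depend on them.

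**It could be left to the SAP.** This does not answer the point. The Protocol does not omit a perspective for later specification. It states one that its described data do not support, and an analysis plan cannot supply data that were not collected.

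**Conclusion.** The point holds in a limited form. Where outcome differences emerge, the Protocol commits to a societal perspective that cannot be met from the data it describes, and a health-service cost reported under that name would be mislabelled. This rests on the described content of the questionnaires and forms being complete as regards cost items, which cannot be verified here.

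The size of the effect cannot be computed. The Protocol gives no figures for employment, time off work or informal care, and nothing shows that these would differ between arms. A reader might infer that comparison C would be the most distorted, because Section 3 expects surgeons to be readier to randomise younger patients to it. That section gives no ages and no employment data, so the inference is speculation and is not part of the finding.

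The effect is confined to the economic evaluation. The Oxford Knee Score analyses, the revision analyses, the sample sizes and the randomisation are unaffected.

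**What to change.** In Section 12, Economic evaluation, replace the societal perspective with an NHS (health-service) perspective. The bracketed term matters because Section 12 collects health care resources without stating that they are limited to the NHS. State that this perspective applies to both the cost-effectiveness and the cost-minimisation branches, since the latter has none at present, and label all cost results accordingly.

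The change is one phrase, one added clause and consistent labelling. It needs no new data. Its cost is a narrower claim: the economic results would speak to health-service costs and not to costs borne by patients, carers or employers.

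If the wider perspective is what is wanted, the text can keep it only by adding the collection and valuation of patient, carer and productivity costs. That means extra questionnaire items over a follow-up planned for at least ten years, which is a much larger change.

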Differences between the groups in revision rates might bias comparisons of the Oxford scores. For this reason these analyses will be run in two ways: firstly on the actual scores at a particular time, irrespective of further surgery (aiming to compare the clinical policies actually used, including repeat surgery); and second, after imputing a score for those who had revision surgery (aiming to compare the initial surgery used in the trial). Although patient survival will be a measure of outcome and described in trial reports, most analyses will be based on the assumption that the alternative prostheses do not have differential effects on mortality. Analyses of the Oxford score will principally be based on survivors but possible effects of excluding those who died will be explored using imputed scores based on the data available. In respect of the revision analyses, participants will be assumed to be at risk only when alive, using a multi-decrement life table approach. It is difficult to predict the proportion of participants who will die or be lost to follow-up, but allowance has been made by aiming to recruit at least 1500, 750 and 400 as applicable.

Additional analyses, stratified by surgeon, will explore any effects of make of prosthesis, surgical experience (‘the learning curve’) and rehabilitation policy.

Timing and frequency of analyses and reporting

Two principal analyses are planned - at six years and then at twelve years.

By six years, participants will have had a median of four years follow-up (assuming it takes six months to initiate the trial, two years to recruit all patients, and six months to complete and report analyses). By this stage, data on early complications, which are likely to be mainly medical, will be available. There will be some early failures, for example due to infection. Outright device failure will be uncommon, but differences in functional scoring could be apparent.

By twelve years, follow-up will have been for a median of ten years. A substantially larger number of device failures and subsequent revisions will have occurred by then.

Confidential interim analyses will be performed at other times as requested by the Data Monitoring Committee, which is expected to meet at least annually (see below).

Economic evaluation

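### The primary economic measure (Oxford Knee Score) does not match the aim of judging what added cost is worth to the NHS, and no cost-per-QALY analysis is committed to

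*Protocol*

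**What the plan says.** The Summary (Aims) gives three bases for judging every comparison: patient-assessed function and health status, reoperation, and "The 'worth' of any additional cost to the NHS".

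Section 7 lists the questionnaire content and gives the reason for one instrument: "the EQ-5D (to derive quality-adjusted life years, QALYs". On timing it says: "The same questionnaire will be completed at three months and then annually (Appendix 5". A baseline EQ-5D value also appears in dummy Table 2A. Deaths are notified through national flagging, and follow-up is planned for at least ten years.

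Section 12 (Economic evaluation) makes the type of analysis depend on the results. With no outcome difference: "If there are no differences in outcome for a particular comparison, cost minimisation analysis will be used". Otherwise: "If differences emerge, cost-effectiveness analyses from a societal perspective will be performed". It then fixes the effect side: "The primary measure of effectiveness will be pain and function as assessed by the Oxford Knee Score". EQ-5D follows in one sentence: "Information on utilities will also be available for analysis because trial patients will also complete EQ-5D for which population-weighted values are available".

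Under Modelling, Section 12 bases the primary economic analysis on resource volumes and revision rates during follow-up. It names revision, resource use and risk factors as the trial data that will set parameters beyond follow-up. Utilities are not named.

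**The concern.** The protocol positively chooses a primary economic measure, so this is not detail left to an analysis plan. The choice sits badly with two other statements in the same document: the aim of judging worth to the NHS, and the reason given for collecting EQ-5D.

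A ratio of extra cost to extra OKS points tells a payer whether an option is worth buying only if someone has said what a point is worth. The protocol gives no such value or threshold. Costs are gathered from theatre through to revision over the whole follow-up, but the protocol does not say how the OKS is to be accumulated over that period. A cumulative cost could therefore be set against an effect that carries no duration.

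Two things are at stake. The headline economic result may not answer the stated question. And because two candidate effect measures are collected and only the less suitable is fixed as primary, the emphasis given to the QALY result could be settled after the data are seen.

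**Working it through.** The protocol states no figure for this point, so there is none to reproduce. The check sets the statements side by side and then illustrates the role of duration.

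**Statements compared**

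| Element | Where | What is fixed |
|---|---|---|
| Question | Summary, Aims | Worth of added NHS cost |
| Reason for EQ-5D | Section 7 | To derive QALYs |
| Primary economic effect | Section 12, Economic evaluation | OKS |
| Role of utilities | Section 12, Economic evaluation | Available; no QALY analysis promised |
| Period of costs | Section 12, Economic evaluation | Initial admission to end of follow-up, then modelled |
| Accumulation of OKS over that period | – | Not specified |
| Value of an OKS point | – | Not specified |

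The first two rows point to QALYs. The third points elsewhere, and the last two show that nothing bridges the gap.

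**Illustration of duration**

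Inputs:
- Gain of 3.0 OKS points: the target difference for three of the four comparisons in Section 12.
- Added cost ΔC = 500: assumed.
- Utility gain u = 0.01 to 0.03 per year, constant while the gain lasts: assumed. The protocol gives no link from OKS to utility.
- Discount rate r = 0, 3.5% or 6%: assumed.
- For the OKS ratio only, the effect is read as a mean difference at one time: assumed, because Section 12 does not say.

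Formulas:
- Cost per OKS point = ΔC / difference.
- Cost per QALY = ΔC / (u × D), where D is the sum of 1/(1+r)^t for t = 0 to T−1 and T is the number of years the gain lasts.

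Results:
- Cost per OKS point: 500 / 3.0 = 167, for T = 1 and for T = 10.
- Cost per QALY, T = 1 (D = 1): 500 / 0.03 = 16,667 to 500 / 0.01 = 50,000.
- Cost per QALY, T = 10, r = 0 (D = 10): 500 / 0.30 = 1,667 to 500 / 0.10 = 5,000.
- Cost per QALY, T = 10, r = 3.5% (D = 8.608): 1,936 to 5,809.

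The one-year figure divided by the ten-year figure is D itself: 10.0 undiscounted, 8.6 at 3.5% and 7.8 at 6%. ΔC and u cancel, so this factor depends only on the two durations, the discount rate and a constant yearly gain. The absolute costs per QALY depend wholly on the assumed ΔC and u.

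**The case against.** The best case for the protocol is that the OKS is the principal outcome and the one the trial is powered on. Section 12 ties the extra cost of mobile bearings to a clear benefit and expresses that benefit as 3.0 OKS points. The protocol does not define worth as comparability with other NHS spending. For choosing between two versions of one operation, a knee-specific effect is coherent. That stands as a defence of reporting cost per OKS point. It does not supply a value for a point, nor explain why an instrument collected to derive QALYs has no committed QALY analysis.

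A reader might infer more than the document supports:

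- **That the trial cannot judge worth.** It can. Utilities are kept available, EQ-5D is repeated annually and deaths are flagged, so QALYs are obtainable.
- **That an early gain fading by year ten would count for nothing.** Section 12 does not say the economic OKS is a single late reading. The first principal analysis, at a median of four years' follow-up, would fall while such a gain was present. How the OKS is summarised could also be left to an analysis plan, which is not at hand.
- **That revised knees would simply show restored scores.** Section 12 also runs the Oxford score analyses with a score imputed for patients who had revision.
- **That deaths are ignored.** The text says "Analyses of the Oxford score will principally be based on survivors", but the same sentence goes on to explore the effect of excluding deaths by imputation. Most analyses also assume no differential mortality, under which valuing survival would probably add little to a between-group difference.
- **That the model has no outcome.** Revision is one. Utilities are unnamed, not excluded.

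If no outcome difference is found, cost minimisation applies and the effect measure is not used. The mismatch therefore matters only when outcomes differ, which is when worth has to be judged.

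**Conclusion.** The point holds as a mismatch between aim and primary measure. The protocol should be changed, though no data are lost and the question remains answerable. The conclusion that the OKS is primary, that utilities are only available, and that neither a value per point nor accumulation over time is specified rests on the text alone.

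The size is illustrative. If the OKS effect is read at one time, cost per point does not separate a one-year gain from a ten-year gain, while cost per QALY differs about 8- to 10-fold for a constant gain. If the OKS were accumulated over follow-up, that loss of duration would go, but the missing value per point would remain. Nothing here shows that any option would be found cost-effective or not: the utility gain is assumed and no standard error is attached to it.

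**What to change.** In Section 12 (Economic evaluation), replace the sentence that makes the OKS primary with wording such as:

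*Effectiveness in the economic evaluation will be measured primarily in QALYs, calculated from EQ-5D at baseline, three months and each year as the area under the curve, with zero from the date of death, over the same period as costs. Cost per OKS point will be reported as a secondary result.*

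Under Modelling, add EQ-5D utilities to the trial data that set the model's parameters.

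The cost is wording only. EQ-5D is already planned at every one of these times and deaths are already notified. The OKS stays the principal clinical outcome, so the sample sizes and the power table do not change. The downside is that EQ-5D may respond less to knee change than the OKS, so intervals for incremental QALYs may be wider. Keeping the OKS ratio as secondary preserves the knee-specific result.
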